### 2.12. Laboratory data

Imaware would be providing the aggregated data sheet with the results after the tests have been analyzed at their laboratories.

Table 2-2. Laboratory parameters to be investigated by the Imaware.

| Lipids | Inflammatory markers | Glucose |
|--------|----------------------|---------|
| TC     | Hs-CRP               | GLU     |
| LDL    |                      | HbA1c   |
| HDL    |                      |         |
| VLDL   |                      |         |
| TG     |                      |         |

TC = Total Cholesterol: LDL = low-density lipoprotein; HDL = high-density lipoprotein; VLDL = very low-density lipoprotein; TG = triglycerides; Hs-CRP = high sensitivity C-reactive protein; GLU = glucose; HbA1c = glycosylated hemoglobin

### 3. Sample size calculation

Power and sample size calculation was performed on the primary outcome (triglycerides) using G\*Power 3.1 (Department of Psychology, University of Düsseldorf, Germany). Sample size calculation was based on a student t-test (two independent samples). Using an effect size of 0.5, and an allocation ratio N2/N1 of 1, the sample size was estimated to be 210 to achieve a power of 95%.

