### 1. Introduction

This statistical analysis plan (SAP) describes all planned analyses for the Clinical Study Report (CSR) of study **ALM-CVH-22**, a multi-center, single arm, open-label post-market evaluation of orally dosed Almega PL on cholesterol and cardiometabolic parameters.

The content of this SAP is based on protocol **ALM-CVH-22** Amendment version 2. All decisions regarding final analysis, as defined in the SAP document, have been made prior to database lock of the study data.

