Along with the fist supplement order shipped to the new subscriptions, participants will receive the baseline hearth health test kit from ImawareTM. Participants will be contacted 3 and 6 months after and they will be sent subsequent kits once the confirmed adherence to the supplement. The test kits will monitor blood lipid levels across a supplementation period (baseline, month 3 and month 6) thanks to a finger prick blood drawing system. The age, height, weight, gender, fasting total cholesterol, LDL-cholesterol, HDL-cholesterol, calculated VLDL-cholesterol, triglycerides, as well as hs-CRP inflammatory marker, and glucose and HbA1c as diabetes indicator of each participant will be recorded over the study period. **Qualitas Health** will receive the aggregated data of the participants only for statistical analyses at their headquarter in Houston and store it in the company share drive with access restricted to those involved in the study. There will be no cost incurred for this analytical assessment to the participant.

Results for the per intended-to-treat (ITT) population will be first tested for normality before any other test will be conducted and baseline data was compared against month 3 and month 6 data. Based on the distribution of data, either Welch two-sample unequal variance t-tests or Wilcoxon Ranks sum tests will be used to compare two-tailed differences between groups. Differences will be considered statistically significant at a p value < 0.05, but the thresholds for the significance of the 20 clinical outcomes were adjusted for multiple variables by the Bonferroni adjustment method which decrease the significance of p-value from <0.05, down to <0.0025. Intervention

effect will also test using an analysis of covariance model (ANCOVA) adjusting for baseline parameters.

[figure not shown]

Figure 1-1 Study design

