### 1.1. Study objectives and endpoints

4-Mar-2022

The aim of this study is to assess the effectiveness of Almega®PL on improving blood markers associated with heart health of iwi customers. Specifically, we would like to confirm the decrease in cholesterol observed in our previous trial (Rao et al., 2020) while assessing the capacity to also decrease triglycerides (primary outcome). As a secondary objective we would like to understand if EPA, precursor of signalling molecules involved in the inflammatory response, could help decrease the inflammatory marker hs-CRP.

Objectives and related endpoints are described in Table 1-1 below

Table 1.1-1. Objectives and relative endpoint

| OBJECTIVES   | ENDPOINTS   | JUSTIFICATION FOR ENDPOINTS   |
|--|---|---|
| Primary  |   |   |
| Can Almega® PL
supplement decrease
triacylglycerides in a
generally healthy
population?  | Triglyceride change from baseline over 6-month period.  | Triglyceride levels is an
atherogenic lipid and an
important risk factor in
cardiovascular disease   |
| Secondary  |   |   |
| Can Almega® PL supplement replicate the decrease in VLDL and total cholesterol we observed in our previous clinical trial (Rao et al., 2020)? Will the results from a controlled population translate to the iwi costumers? Can Almega® PL | Total Cholesterol change from baseline over 6-month period. VLDL-Cholesterol change from baseline over 6-month period. LDL-Cholesterol change from baseline over 6-month period. HDL-Cholesterol change from baseline over 6-month period. hs-CRP change from baseline over 6-month period. Fasting glucose change from baseline over 6-month period. HbA1c change from baseline over 6-month period. | Cholesterol in plasma levels is atherogenic and a risk factor in cardiovascular disease. Hs-CRP is an age-related inflammatory market. Omega-3 help regulate the inflammatory response. |

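### The sample size of 210 for 95% power belongs to a two-group trial; this trial has one arm and a within-person endpoint, and the planned two-sample tests repeat the mismatch

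*SAP*

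**What the plan says.** - **Sample size (SAP section 3).** "Sample size calculation was based on a student t-test (two independent samples"), for triglycerides, with effect size 0.5 and an allocation ratio of 1; "the sample size was estimated to be 210 to achieve a power of 95" per cent. The section states no alpha, sidedness, SD, triglyceride change in laboratory units, or source for the 0.5.
- **Design (SAP section 1).** The study is "a multi-center, single arm, open-label post-market evaluation of orally dosed Almega PL". Protocol section 9 also describes one open-label arm, with 200-300 participants.
- **Primary endpoint (SAP Table 1.1-1).** "Triglyceride change from baseline over 6-month period".
- **Comparison and tests (SAP 1.1, Study design).** "baseline data was compared against month 3 and month 6 data", and "either Welch two-sample unequal variance t-tests or Wilcoxon Ranks sum tests will be used to compare two-tailed differences between groups". Protocol section 9 names the same two tests. Both documents add an ANCOVA adjusted for baseline.
- **Significance level.** Protocol section 9 uses 0.05. SAP 1.1 applies a Bonferroni adjustment for 20 outcomes, to "decrease the significance of p-value from <0.05, down to <0.0025".
- **Who supplies a pair.** For the follow-up kits, SAP 1.1 says of participants that "they will be sent subsequent kits once the confirmed adherence to the supplement". SAP 2.6 discontinues anyone without a baseline result. SAP 2.7.2 admits to the ITT set anyone with a baseline and at least one later test, including people with month 3 only.

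**The concern.** Every participant supplies both the baseline and the follow-up value, so there is no second group and nothing to allocate. A between-group effect size of 0.5 does not say what mean change, relative to what SD of change, the trial was planned to detect. The 95% therefore cannot be read as this trial's power.

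The primary analysis has the same fault. Welch and rank-sum tests assume two independent samples. Applied to two measurements of the same people, they ignore the within-person correlation. If it is positive, the standard error is too large, the p-values are too large and power is lost.

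Three further gaps have to be closed before a correct power statement can be written:
- The alpha implied by 210 is not the 0.0025 in SAP 1.1.
- Neither month 3 nor month 6 is named as primary for triglycerides.
- No number of evaluable pairs is given, although the documents describe several ways in which pairs are lost.

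**Working it through.** **1. Reproducing 210.** Inputs from SAP section 3: d = 0.5, ratio 1, power 95%. Two-sample t-test, noncentral t with noncentrality d·√(n/2) and 2n − 2 degrees of freedom:
- Two-sided 0.05: 104 per group gives 94.83% and 105 per group gives 95.01%, so the total is 210. It reproduces.
- One-sided 0.05 gives 176 in total, two-sided 0.0025 gives 354 (177 + 177), and a paired test with standardised change 0.5 gives 54. None returns 210.

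Two-sided 0.05 is thus inferred. At 0.0025 the same two-group method with 105 per group has 71.2% power. Neither 95.0% nor 71.2% is this trial's power.

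**2. Power of the matching paired test.** Let d be the mean change in between-person SD units and r the within-person correlation. With equal variances the SD of change is σ√(2(1 − r)), so dz = d/√(2(1 − r)). For d = 0.5, dz = 0.354, 0.423 and 0.500 at r = 0, 0.3 and 0.5. Noncentrality is dz·√n with n − 1 degrees of freedom.

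The documents give neither r nor a retention rate. Assumed pairs are 210 (70% of 300), 140 (70% of 200) and 100 (50% of 200).

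| Pairs | 0.0025, r = 0 | 0.0025, r = 0.3 | 0.0025, r = 0.5 | 0.05, r = 0 |
|---|---|---|---|---|
| 210 | 98.0% | 99.9% | >99.9% | 99.9% |
| 140 | 86.2% | 97.1% | 99.7% | 98.6% |
| 100 | 66.7% | 86.5% | 96.9% | 93.8% |

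Pairs needed for 95% power at r = 0 and r = 0.5: 106 and 54 at 0.05; 179 and 92 at 0.0025.

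**3. What the unpaired test does to paired data.** Welch takes the variance of the mean difference as 2σ²/n, but the true value is 2σ²(1 − r)/n. Its statistic therefore has SD √(1 − r) instead of 1. With no true change, a nominal 5% test rejects with probability 2[1 − Φ(1.96/√(1 − r))]:
- r = 0.3: 1.96/0.837 = 2.34, giving 1.9% (simulated 1.8%).
- r = 0.5: 1.96/0.707 = 2.77, giving 0.56% (simulated 0.59%).

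Simulated power at d = 0.5 and alpha 0.0025 (40,000 bivariate normal trials), Welch v paired t:

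| Pairs | r = 0.3 | r = 0.5 |
|---|---|---|
| 210 | 99.3% v 99.9% | 99.9% v 100% |
| 140 | 91.1% v 97.2% | 94.2% v 99.7% |
| 100 | 71.3% v 86.5% | 74.5% v 96.8% |

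At r = 0 there is no loss. At alpha 0.05 and r = 0.5 the loss is small even with 100 pairs (98.6% v 99.9%). Rank-sum v signed-rank behaves like Welch v paired: 70.0% v 95.9% with 100 pairs, r = 0.5, alpha 0.0025 (4,000 trials).

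**4. If the true change is smaller than 0.5 SD.** Assume 0.2 SD, r = 0.5 and 210 pairs, with Welch power approximated by Φ[(d/√(2/n) − z)/√(1 − r)]. Here 0.2/√(2/210) = 2.049.
- Alpha 0.05: (2.049 − 1.960)/0.707 = 0.13, so Welch 55%; paired 82%.
- Alpha 0.0025: (2.049 − 3.023)/0.707 = −1.38, so Welch 8%; paired 44%.

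**The case against.** - **The tests err on the safe side and the trial is not shown to be too small.** Both are true, and at d = 0.5 with 210 pairs the loss from the unpaired tests is negligible. But a conservative test can miss a real change, and step 4 shows that the loss is large with all 210 pairs if the change is nearer 0.2 SD.
- **The 74% v 97% contrast stacks assumptions:** 100 pairs, r = 0.5, and 0.0025 applied to triglycerides. This is fair, and each is an assumption. Whether 0.0025 governs the primary endpoint is itself unclear: SAP 1.1 speaks of 20 outcomes, while Table 1.1-1 lists eight endpoints. That supports asking the sponsor to name one alpha.
- **Month 6 is the natural reading of the endpoint.** It is the likelier one, since the final blood test is at month 6. It is nowhere stated as primary, month 3 is also tested, and the ITT set includes people who have only month 3.
- **The ANCOVA could rescue the analysis.** With one arm there is no treatment term. A regression of change on centred baseline would estimate the mean change through its intercept, but neither document says that this is meant.
- **The protocol and SAP alphas may reflect different versions.** This is possible, since the SAP cites an amended protocol. The conflict between sections 1.1 and 3 of the SAP remains.

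**Conclusion.** The concern holds and should be fixed. The design basis of the sample size is wrong although its arithmetic is right, and the planned primary tests do not suit paired data. Neither conclusion depends on any assumed figure.

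The size of the harm does depend on assumptions. At the SAP's effect size of 0.5, it runs from nothing (r = 0) or negligible (210 pairs) to about 22 percentage points of power (100 pairs, r = 0.5, alpha 0.0025). It is larger if the true change is smaller. The finding does not show that recruitment is inadequate. Adequacy cannot be judged for any other effect until the sponsor states the mean change and the SD of change.

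**What to change.** 1. **SAP section 3.** Delete the two-sample basis and the allocation ratio, and write: *Power is for a two-sided paired t-test of triglyceride change from baseline to [primary time point] at alpha [X]. Assuming a mean change of [D] and an SD of change of [S] (source stated), [N] evaluable pairs, [Y]% of those enrolled, give [P]% power.* As a check on the entries, 95% power requires these D/S values:

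| Pairs | alpha 0.05 | alpha 0.0025 | 95% CI half-width for mean change (SD of change) |
|---|---|---|---|
| 210 | 0.25 | 0.33 | 0.14 |
| 140 | 0.31 | 0.40 | 0.17 |
| 100 | 0.36 | 0.48 | 0.20 |

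2. **Alpha and time point.** Name one of each for triglycerides, and bring Protocol section 9 and SAP 1.1 into line. If month 6 is chosen, say how participants with only a month-3 value are handled, because a month-6 pair excludes them.
3. **Tests, in SAP 1.1 and Protocol section 9.** Replace Welch and rank-sum with the paired t-test and the Wilcoxon signed-rank test, and report the mean change with its confidence interval. Drop the ANCOVA or restate it as a baseline-adjusted model of change.

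**Cost.** One rewritten paragraph, one sentence on alpha and time point, and changed test names in two places. The edits themselves require no added participants, visits or blood tests. One practical condition applies: SAP 1.1 and 2.12 describe the laboratory data as aggregated, so the data sheet must carry the study number mentioned in Protocol 10.5. Without it, a person's results cannot be paired.
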